## **6.2 PREPARATION/HANDLING/STORAGE/ACCOUNTABILITY**

### **6.2.1 ACQUISITION AND ACCOUNTABILITY**

All insulins, test strips, glucometers will be supplied to the investigator as a donation from the Australian based non-profit humanitarian organization Life for a Child.

Medications and CGMs will be securely stored at the clinical or medical supply distribution facilities of the BIRDEM hospital located in Dhaka Bangladesh, or the Tanzanian Diabetes Association in Dar Es Salaam, Tanzania.

#### 6.2.2 FORMULATION, APPEARANCE, PACKAGING, AND LABELING

See 6.1.2 above

#### 6.2.3 PRODUCT STORAGE AND STABILITY

For longer term storage, insulin should be kept below 25 degrees C, or per package insert instructions.

#### 6.2.4 PREPARATION

Not applicable.

### 6.3 MEASURES TO MINIMIZE BIAS: RANDOMIZATION AND BLINDING

Randomization: We will use a stratified blocked randomization approach with variable block sizes. Since we aim to conduct a multi-center trial, we will stratify randomization by center, since there will likely be differences in the patient population or clinical practice patterns at each center that may affect the outcome. For example, stratifying randomization by center may also help to protect against imbalances in the distribution of participants who use NPH or 70/30 at baseline, as these choices may reflect local (i.e. center-specific) practice patterns.

The randomization sequence will be prepared in advance by the lead statistician, [name], and integrated into an online, secure, data management system that will be developed specifically for this trial. [name] will use the "blockrand" package in R statistical software to generate the randomization sequence.

Allocation concealment: Local trial staff will use the online data management system developed for this trial to obtain the next randomization sequence. Neither the PI nor the local trial staff will have access to the randomization sequence. Treatment assignment will only occur after a study participant has been determined to meet all inclusion and exclusion criteria (i.e. screening) and completed the baseline study procedures in the run-in phase.

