## 4.2 SCIENTIFIC RATIONALE FOR STUDY DESIGN

NPH or premixed 70/30 is an appropriate control given that this is the current standard of care for the vast majority (over 90%) of youth living with T1D in low resource settings.

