## 5 STUDY POPULATION

### 5.1 INCLUSION CRITERIA

In order to be eligible to participate in this study, an individual must meet all of the following criteria:

1. Children and young adults (age 7-25)
2. Have a clinical diagnosis of type 1 diabetes (T1D)

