### 5.2 EXCLUSION CRITERIA

An individual who meets any of the following criteria will be excluded from participation in this study:

1. Prior use of any insulin analogue
2. Patients (or parents for children <18 years old) who refuse to or cannot provide informed consent
3. Who are currently pregnant or plan to become pregnant over the next year
4. Who have previously used a continuous glucose monitor (CGM) for glucose monitoring
5. Who were first diagnosed with T1D less than 12 months ago
6. Who is diagnosed with severe malnutrition

The rationale for selecting this patient population is threefold: (1) they comprise most of the individuals living with T1D in the settings that Life for a Child (LFAC) supports and where we hope to conduct the trial, (2) it will be difficult to ensure that CGM sensors are not accidentally removed prior to the end of each 14-day measurement period for children under 7 years of age, and (3) this patient population is likely the group that will be treated first with analogue insulins if/when such products are more widely procured globally.

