### 8.2 SAFETY AND OTHER ASSESSMENTS

Study Measurements

Baseline demographics/comorbidities	Description
Age	At time of randomization, in years
Duration of type 1 diabetes	Based on self-report or extraction from medical record, in years
Type of insulin regimen	Generally, as two categories, NPH + regular (basal/bolus regimen) or premixed 70/30
Number of units of insulin per day	Total number of international units of insulin used per day, including all basal and bolus insulins.
Mean HbA1c (%) [SD]	HbA1c laboratory result (units=%), most recent
Complications of Type 1 Diabetes	Clinical presence or absence of diabetic retinopathy, neuropathy, or nephropathy (extracted from medical record)

Hypoglycemic events	Number of episodes of symptomatic hypoglycemic events in the past 12 months
Co-Primary Outcomes:	
Time-in-serious hypoglycemia	% spent less than 54mg/dl, averaged across all daily measures averaged across two CGM sensors starting 6 months after randomization
Time-in-range (TIR)	% between 70 and 180mg/dl inclusive, averaged across two CGM sensors 6 months after randomization
Secondary Outcomes:	
Time-in-hypoglycemia	% spent less than 70mg/dl
Time-above-range	% spent greater than 180mg/dl
Nocturnal hypoglycemic events	Number of events (defined as >=15mins in duration < 70mg/dl) between 1200 and 0600
Glycemic control (HbA1c)	Mean HbA1c lab result at baseline, 3, 6, 9 and 12 months after randomization
Rate of severe hypoglycemic events	Events requiring the assistance of an external third party person
Rate of diabetic ketoacidosis (DKA)	Measured by self-report and confirmed through review of hospital records
Quality of Life (e.g. Fear of Hypoglycemia Survey)	As assessed using validated instruments (PedsQL and Insulin Treatment Satisfaction Questionnaire (ITSQ)).
Adverse Events	
Hypoglycemic events (clinically significant events)	See primary and secondary outcomes above. Insulin in any form is known to be associated with low blood sugars. Therefore, we are measuring this as a primary/secondary outcome...but it also may be considered an adverse event/safety event.
Severe hypoglycemic events (<54mg/dl by CGM) > 10%	In the case severe hypoglycemia exceeds 10% on any CGM sensor, the treating clinician will be notified.
Skin discomfort/irritation	Self-report
Skin infection	Self-report

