#### 9.4.5 BASELINE DESCRIPTIVE STATISTICS

Baseline Characteristic	Glargine	Usual care Human Insulin
Age		
7-10		
10-14		
15-25		
Male sex		
Race		
Asian		
African		
Other		
Country		
Bangladesh		
Tanzania		
Other		
Duration of type 1 diabetes, years, mean [SD]		
Comorbidities		
Retinopathy		
Nephropathy		
Diabetic foot disease		
HbA1c (%), mean [SD]		
Insulin Regimen		

NPH + regular		
Premixed 70/30		
Premixed 70/30 + regular		
Other		
Baseline insulin dose, IU per kg, mean [SD]		
Total		
Basal		

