#### 9.4.7 SUB-GROUP ANALYSES

In recognition of the possibility that treatment effect may vary according to select baseline factors that may influence our clinical outcomes, we will include several planned subgroup analyses. The most important of these will be the patient's insulin prior to randomization (NPH versus 70/30), which allows an unbiased comparison of the glargine versus NPH and the glargine versus 70/30, though admittedly these comparisons will be underpowered. In addition, we will examine whether the treatment effect differs by clinical site (Bangladesh or Tanzania) and when comparing the route of insulin delivery (pens versus syringe and vial). The principal goal of these subgroup analyses will be to check for apparent consistency in the treatment effect of analogue against both potential options within the usual care group. We will also perform subgroup analyses by age groups (e.g. younger vs older children/youth), and baseline hypoglycemia risk.

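### Baseline insulin regimen (NPH or 70/30) is named as an imbalance concern and as the main subgroup factor, but is in neither co-primary model; adding it costs almost nothing and gains a little precision

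*Combined protocol and SAP*

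**What the plan says.** **Randomization (6.3).** Allocation is stratified by center only. Baseline regimen is raised there as a reason for doing so: "stratifying randomization by center may also help to protect against imbalances in the distribution of participants who use NPH or 70/30 at baseline". The argument is that the choice of regimen may follow local practice.

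**Primary analysis (9.4.2).** Both co-primary outcomes use linear regression on treatment, age, site and baseline CGM values. The model for time below 54 mg/dl takes baseline time below 54 and baseline time in range; the time-in-range model takes baseline time in range. Regimen is in neither. Adjustment is justified there on two grounds: covariates related to the outcome raise power, and baseline measurements guard against random imbalance.

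**Subgroups (9.4.7).** Of the planned subgroup analyses, "The most important of these will be the patient's insulin prior to randomization (NPH versus 70/30"). The section concedes low power.

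**Classification.** Section 8.2 records regimen "Generally, as two categories, NPH + regular (basal/bolus regimen) or premixed 70/30". The baseline table in 9.4.5 has four rows, among them "Premixed 70/30 + regular" and a residual Other row. The subgroup in 9.4.7 has two levels.

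**Eligibility (5.1, 5.2).** The inclusion criteria are "Children and young adults (age 7-25") and "Have a clinical diagnosis of type 1 diabetes (T1D"). The only exclusion that concerns insulin type is "Prior use of any insulin analogue". No criterion names a current regimen.

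**The concern.** The plan identifies regimen as a source of imbalance, ranks it first among effect modifiers, and in Section 2.2 associates 70/30 with hypoglycemia, which is one of the two co-primary outcomes. By the plan's own reasons for adjusting, regimen belongs in the models.

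Center can stand in for it in only one situation. If each center uses mainly one regimen, stratifying by center balances regimen, but the NPH-versus-70/30 subgroup then largely repeats the site subgroup. If both regimens are used within a center, the proxy gives little protection and a chance imbalance is neither prevented nor adjusted for. The documents do not show which situation applies.

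At stake is some precision in the co-primary estimates, and a key subgroup factor whose classes are not defined the same way throughout.

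**Working it through.** **Inputs from the plan (9.2).** Control mean 5.8 and SD 6.6 for time below 54 mg/dl; glargine outcome = control × 0.67; 150 per arm; alpha 0.025 per outcome.

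**Inputs assumed.** Share f on 70/30 of 30-50%, mixed within centers. Difference D between regimens in time below 54 of 1 to 3 percentage points. The documents give neither figure.

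**Step 1. The plan's power.**
- Effect = 0.33 × 5.8 = 1.914. SDs are 6.6 and 0.67 × 6.6 = 4.42.
- SE = √((6.6² + 4.42²)/150) = 0.649.
- Power = Φ(1.914/0.649 − 2.241) = Φ(0.709) = 76.1%.
- Simulating from a beta distribution scaled to 0-24 with the same mean and SD gives 77.2%.

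Both are within 2 points of the stated 77.7%, so the inputs are read correctly. Neither check uses covariates.

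**Step 2. Chance imbalance in regimen.** The 95% range is ±1.96 × √(f(1−f) × 2/n), with n per arm.

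| f | 150 per arm | 200 per arm |
|---|---|---|
| 0.3 | ±10.4 points | ±9.0 points |
| 0.5 | ±11.3 points | ±9.8 points |

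At 150 per arm, the chance of an imbalance above 10 points is 5.9% (f = 0.3) to 8.3% (f = 0.5).

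**Step 3. What that does to the estimate.** Shift in the unadjusted estimate = D × imbalance. At the 95% limit this runs from 1 × 0.104 = 0.10 to 3 × 0.113 = 0.34 points. Against the planned 1.914 that is 5% to 18%. The shift averages zero over randomizations and is already part of the standard error.

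**Step 4. Power gained by adjusting, with no credit for baseline CGM.** Variance explained by regimen is R² = f(1−f)D²/6.6².
- f = 0.3, D = 1: R² = 0.0048, power 76.3%.
- f = 0.5, D = 3: R² = 0.0517, power 78.5%.

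The gain over 76.1% is 0.2 to 2.4 points.

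**Step 5. Power gained on top of baseline CGM.** Assume the regimens differ by the same D at baseline and that baseline and follow-up correlate at ρ within regimen. The residual variance factor is 1 − (ρ(1−R²) + R²)² with baseline alone, and (1−R²)(1−ρ²) with baseline and regimen. At f = 0.5 and D = 3, the most favorable case:
- ρ = 0.3: 81.4% rises to 82.5%, a gain of 1.1 points.
- ρ = 0.5: factors 0.723 and 0.711; 89.0% rises to 89.6%, a gain of 0.6 points.
- ρ = 0.7: 97.6% rises to 97.7%, a gain of 0.1 points.

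Smaller f or D gives less.

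**Step 6. Regimen classes side by side.**

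| Section | Classes |
|---|---|
| 8.2 | NPH + regular; 70/30 |
| 9.4.5 | NPH + regular; 70/30; 70/30 + regular; Other |
| 9.4.7 | NPH; 70/30 |

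The two 70/30 rows in 9.4.5 fit naturally under one heading, but no section says so, and Other has no stated place in the subgroup analysis.

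**The case against.** The case for leaving the plan alone is strong. Prior insulin is fixed before randomization, so glargine against control within each regimen is a randomized comparison without a regimen stratum; 9.4.7 is right to call it unbiased. For the primary comparison, chance imbalance is already in the standard error, and site and baseline CGM absorb part of it. The sponsor considered regimen balance in 6.3 and claimed only that center stratification may help. All of this stands, and it limits the point to a small gain.

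A reader might also infer a larger flaw: that because eligibility names no regimen, the trial will enroll controls who are not the stated comparator. The documents do not support that.
- The objective in Section 3 gives NPH and 70/30 as examples of standard-of-care human insulin. Narrower wording appears in the study description in 1.1, in 4.1 and in 6.1.2, but the objective itself is open.
- A participant on regular insulin alone is hypothetical. Prior analogue users and those diagnosed less than 12 months ago are excluded, and 6.1.2 describes regular as the mealtime insulin. The Other row could equally hold NPH alone or NPH with 70/30.
- Section 4.2 says of NPH or 70/30 that "this is the current standard of care for the vast majority (over 90%) of youth living with T1D in low resource settings". It does not follow that up to 10% of participants use neither, because the remainder of that wider population can include analogue users, whom 5.2 excludes.

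What remains is that the text does not say how such a participant would be handled, should one exist.

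**Conclusion.** The point holds as a low-cost improvement. Regimen meets the plan's own reasons for adjustment, is collected at baseline, and is missing from both co-primary models, while the center proxy rests on a pattern that the documents do not show.

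The size is small. With 30-50% on 70/30 mixed within centers and regimens differing by 1-3 points in time below 54, the gain is 0.2 to 2.4 power points before crediting baseline CGM, and at most about 0.6 points once baseline and follow-up correlate at 0.5 or more. If regimen follows center, the site covariate already does the work and the gain is close to nil. The time-in-range gain was not calculated.

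The omission should not be read as biasing the primary or subgroup comparisons, or as undermining the sample size; neither follows. The differing regimen classes are missing detail rather than a contradiction in the analysis.

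**What to change.** 1. **Section 9.4.2.** Before outcomes are compared by arm, add baseline insulin regimen as a fixed covariate in both co-primary models, in three classes: NPH-based; 70/30-based, with or without regular; other.
2. **Sections 8.2, 9.4.5 and 9.4.7.** Use the same three classes throughout. State where NPH alone and NPH combined with 70/30 belong. Keep participants classed as other in the intention-to-treat set and leave them out of the NPH-versus-70/30 subgroup.
3. **Sections 5.1-5.2 and 6.1.2.** The investigators should reconcile the eligibility criteria with the glargine starting-dose text and the control-arm text for any participant whose baseline regimen is neither NPH nor 70/30. No clinical rule is proposed here.

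A new inclusion criterion on current regimen is not recommended. The amendment log runs to version 6.0 of July 2024, and 6.1.2 describes an insulin supply change made in January 2024, so such a criterion may reach few further entrants. It would also narrow a sample that 5.5 says is meant to resemble ordinary practice.

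**Cost.** One degree of freedom per model, or two if anyone is classed as other, and a short amendment. The data are already collected and randomization is unchanged. Because the trial is open-label, the change should be dated and fixed before any comparison of outcomes by arm.

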### 6.4 STUDY INTERVENTION COMPLIANCE

Adherence to both study interventions and use of CGMs will be assessed at each home and clinic visit using electronic case report forms.

We will measure adherence to the study interventions by asking each participant during all clinic and home visits what type(s) of insulin they are currently using. To monitor adherence, staff will also ask how many units of each insulin and total insulin dose (if participant is using more than 1 type of insulin)

the participant takes per day during all clinic and home visits. To confirm adherence, staff will ask to see the participant's insulin vials or cartridges.

Use of CGMs and any potential sensor malfunctions will be directly assessed in person (or by telephone) by local trial staff.

## 6.5 CONCOMITANT THERAPY

We will also assess whether any non-study insulin analogues have been introduced or used by any participant during follow-up.

### 6.5.1 RESCUE MEDICINE

The study site will supply glucagon as a rescue medication that will be provided by the sponsor to all participants. The use of rescue medications is allowable at any time during the study. Training on use of the nasal or injectable glucagon will also be provided at the time of dispensing. The date and time of rescue medication administration as well as the name and dosage regimen of the rescue medication will be recorded.

## 7 STUDY INTERVENTION DISCONTINUATION AND PARTICIPANT DISCONTINUATION/WITHDRAWAL

### 7.1 DISCONTINUATION OF STUDY INTERVENTION

Discontinuation from the study intervention does not mean discontinuation from the study, and remaining study procedures should be completed as indicated by the study protocol. For example, a participant may decide that they would like to go back to their previously used human insulin regimen. During the study, participants will be encouraged to stay on their randomly assigned treatment group, unless there is a clinical reason to switch (i.e. cross-over).

At the end of this study, participants will be given the opportunity to switch to the contralateral treatment group if they would like to (and the treating provider agrees).

### 7.2 PARTICIPANT DISCONTINUATION/WITHDRAWAL FROM THE STUDY

Participants are free to withdraw from participation in the study at any time upon written request. An investigator may discontinue or withdraw a participant from the study for the following reasons:

- If any clinical adverse event (AE), laboratory abnormality, or other medical condition or situation occurs such that continued participation in the study would not be in the best interest of the participant
- Disease progression which requires discontinuation of the study intervention
- If the participant meets an exclusion criterion (either newly developed or not previously recognized) that precludes further study participation

The reason for participant discontinuation or withdrawal from the study will be recorded on the Case Report Form (CRF). Subjects who sign the informed consent form and are randomized but do not receive

the study intervention (e.g. did not receive their randomly assigned medication) may be replaced. Subjects who sign the informed consent form, and are randomized and *receive* the study intervention, and subsequently withdraw, or are withdrawn or discontinued from the study, will not be replaced.

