**Incomplete or missing CGM Sensor Data:** Even though returning a baseline CGM sensor (i.e. the one placed during the run-in phase) is one of the trial eligibility criteria, it is expected that some participants may have incomplete or missing CGM sensor data. For example, a CGM sensor could fall off accidentally before the end of each 14 day sensor wear period. Such sensors may also be lost before study staff have an opportunity to download the glucose data.

If a CGM sensor falls off early, or presents with no data due to a sensor download error, or is accidentally removed less than 9.8 days (70% of 14 days; consistent with international consensus recommendations on the use of CGMs in clinical trials), they may receive a replacement sensor. If a participant is able to successfully wear a sensor for 14 days, but a sensor shuts-off early (e.g. only 6 days of glucose measurement data is captured), they will not have a replacement sensor. Rationale: randomization should balance incomplete sensor data across the two study arms.

In the *primary* analysis, we will include all available sensor data (regardless of the duration of sensor wear or the number of days of glucose measurements) collected while enrolled in the study. In a *sensitivity* analysis, we will include only sensors with at least 70% of data availability during each 14 day wear period (i.e.  $\geq 9.8$  days). In another *sensitivity* analysis, we will impute for missing data. In an exploratory analysis, we will include data from 12-month follow-up replacement sensors that were collected after a participant completed study.

**Lost to follow-up:** If a participant discontinues before any of the follow-up CGM data are recorded (e.g. participant has no recorded CGM data at all during follow-up) they will not contribute data to the primary efficacy analysis. As described above, we are planning the study to have sufficient power with a usable analytic sample of  $n=300$  participants. We propose to recruit  $n=400$  participants, which allows for up to 25% attrition (participants that are lost shortly after randomization, before any CGM data have been collected) while retaining sufficient power to test our primary hypothesis.

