In recognition of the fact that in some cases a participant’s discontinuation could represent a negative clinical outcome, we will perform several sensitivity analyses to ensure that we are thorough and transparent in reporting the possible effects that the missingness would have on our primary analysis. The first sensitivity analysis will be multiple imputation analysis, imputing the missing outcome data based on observed baseline data; this approach is preferred to single-imputation (e.g. last observation carried forward or assign-the-worst) as it takes into account residual uncertainty in the missing values. The second sensitivity analysis will be a win-ratio analysis where participants that died during the study are ranked as having the worst possible outcome; participants that discontinued study participation due to an adverse event are ranked as having the second worst outcome value; participants that discontinued with no known adverse event are ranked as having the third worst outcome value; and participants that return complete CGM data during the intensive follow-up period are ranked according to their % time-in-serious-hypoglycemia ( $<54$  mg/dl), with higher scores representing worse outcomes. This approach provides an estimate of which treatment arm led to better overall outcomes while including death, discontinuation, and hypoglycemia into a single composite outcome measure. This will

not be the primary analysis due in part to difficulty interpreting the results and the emphasis on glycemic control as the most important outcome in this therapeutic trial, but it will provide an important check that any observed benefits on a time-in-serious-hypoglycemia outcome or the time-in-range outcome are not offset or explained by greater death or discontinuation in the other treatment arm.

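### Section 7.2 allows withdrawal from the study for disease progression that stops the assigned insulin, which Section 7.1 says is not a reason to leave follow-up

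*Combined protocol and SAP*

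**What the plan says.** Section 7.1 states the principle: "Discontinuation from the study intervention does not mean discontinuation from the study, and remaining study procedures should be completed". It gives the example of a participant returning to the previous human insulin, and it treats a switch made for a clinical reason as a cross-over within the trial.

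Section 7.2 concerns leaving the study altogether. It opens with "An investigator may discontinue or withdraw a participant from the study for the following reasons" and lists three grounds. The second is "Disease progression which requires discontinuation of the study intervention". The first begins "If any clinical adverse event (AE), laboratory abnormality, or other medical condition or situation occurs" and carries a condition: "such that continued participation in the study would not be in the best interest of the participant". The third, meeting an exclusion criterion, is not at issue here.

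Section 9.3 names one population, all randomized participants. Sections 8.2 and 9.4.2 take both co-primary values from the two sensors worn in months 6-7, and 9.4.2 uses data collected while the participant is enrolled. Of participants who discontinue before any follow-up CGM is recorded, 9.4.2 says "they will not contribute data to the primary efficacy analysis". It accepts that discontinuation may be a bad outcome and adds two sensitivity analyses: multiple imputation from baseline data, and a win ratio in which "participants that discontinued study participation due to an adverse event are ranked as having the second worst outcome value".

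**The concern.** A site that follows 7.1 keeps such a participant in visits and CGM wear. A site that follows 7.2 may end both. Disease progression is not defined for this population, so sites may also differ on when the bullet applies.

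The choice matters because it decides who has a co-primary value. The trial is open-label, so the person deciding knows the arm. The argument in Section 4.1 that blinded sensors protect the outcome covers how glucose is measured, not who is still there to be measured. Section 8.2 says of hypoglycemia that "we are measuring this as a primary/secondary outcome...but it also may be considered an adverse event/safety event", so the condition that prompts a decision can be the outcome itself. Losing participants for that reason biases the comparison in a direction that depends on which arm loses more. The 25% attrition allowance protects power but not against this bias.

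**Working it through.** **1. The two sections side by side**

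| Event | Section 7.1 | Section 7.2 |
|---|---|---|
| Assigned insulin stopped or switched for a clinical reason | Stays in the study; procedures continue | If called disease progression, may be withdrawn from the study |
| Adverse event, laboratory abnormality or other condition | Not addressed as such | May be withdrawn only if continued participation is not in the participant's best interest |

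The first row is a conflict. The second is not: that ground turns on study participation, not on stopping insulin. It does, however, fail to separate stopping insulin from stopping follow-up.

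**2. From withdrawal to a missing co-primary value**

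Both endpoints are defined on months 6-7. Withdrawal before then leaves no value for either regression; withdrawal after month 7 costs no co-primary data. The imputation uses baseline data only, so it cannot reflect the glycemia after randomization that prompted the exit. The win ratio ranks completers on time below 54 mg/dl only, so it does not cover time in range (TIR).

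**3. The plan's own figure**

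Inputs from Section 9.2: control mean 5.8, SD 6.6, maximum 24; glargine is control times 0.67; 150 per arm; alpha 0.025, taken as two-sided.

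- Difference: 5.8 × 0.33 = 1.914 points.
- Pooled SD: √[(6.6² + (0.67 × 6.6)²)/2] = 5.62.
- Standard error: 5.62 × √(2/150) = 0.649.
- Power: Φ(1.914/0.649 − 2.241) = 76.1%, against 77.7% stated. The inputs are read correctly.

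**4. Illustration of the bias**

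Assumptions, none from the documents: 5% of controls and no glargine participants are withdrawn before month 6; the chance of withdrawal is proportional to time below 54 mg/dl; the baseline-outcome correlation r is 0.3 to 0.7; baseline SD is 6.6 in both arms.

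*Unadjusted, withdrawal tracking the outcome.* The control mean falls by w/(1 − w) × SD²/mean = (0.05/0.95) × (43.56/5.8) = 0.395 points. As a share of the effect, 0.395/1.914 = 20.7%.

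*Adjusted for baseline time below 54 mg/dl.* The within-arm slope is r in controls and 0.67r in glargine, on average 0.835r.

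- Withdrawal tracks the outcome: the shift is 0.395 × (1 − 0.835r²). At r = 0.3 it is 0.366 (19.1%); at r = 0.7 it is 0.234 (12.2%).
- Withdrawal tracks baseline: the shift is 0.395 × r × (1 − 0.835). At r = 0.3 it is 0.020 (1.0%); at r = 0.7 it is 0.046 (2.4%).

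Simulation with a scaled-beta outcome (24 × Beta, matched to mean 5.8 and SD 6.6) gives about 13-19% and about 0-2%. The hand formula differs slightly because it holds the slope at its value before withdrawal.

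*Reverse direction.* With 5% of glargine and no controls withdrawn, tracking the outcome, the glargine mean falls by 0.67 × 0.395 = 0.265, an unadjusted inflation of 13.8%. After adjustment it is 0.265 − 0.835r² × 0.395: 0.235 (12.3%) at r = 0.3 and 0.103 (5.4%) at r = 0.7.

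*Effect on power.* At the standard error above, shrinkage of 13% gives Φ(0.87 × 2.949 − 2.241) = 63%, and 19% gives Φ(0.81 × 2.949 − 2.241) = 56%.

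Age, site and baseline TIR, which are also in the planned model, are not in this illustration. The TIR endpoint was not quantified.

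**The case against.** The sponsor can fairly say that the wording is permissive, that the bullet may rarely be used, and that both arms receive insulin, so disease progression that ends the intervention is hard to picture. For hypoglycemia the plan describes responses other than withdrawal: individual titration (4.3), glucagon (6.5.1), and notice to the treating clinician when time below 54 mg/dl exceeds 10% on a sensor (8.2). The primary model adjusts for baseline, and two sensitivity analyses address discontinuation. All of this stands. It limits the likely size but does not remove the conflict.

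Four stronger readings are tempting, and the documents do not support them.

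- That the adverse-event ground also contradicts 7.1. It does not, because of its best-interest condition.
- That hypoglycemia will lead to withdrawal at some known rate. No section says so.
- That the lost-to-follow-up rule in 9.4.2 excludes everyone withdrawn before month 6. It concerns participants with no follow-up CGM at all. The plan is unclear about someone with a month-3 sensor only; what leaves that person without a co-primary value is the month 6-7 definition.
- That the effect would shrink by about 21%. That is the unadjusted figure, with withdrawal driven by an outcome not yet observed when the decision is made.

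**Conclusion.** The conflict between 7.1 and the disease-progression bullet in 7.2 is in the text and does not depend on any calculation. Its consequence, a missing co-primary value for anyone withdrawn before month 6, follows from the endpoint definition.

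The size is uncertain. At an assumed 5% versus 0%, the adjusted effect on time below 54 mg/dl shrinks by about 0-2% in the mild case and about 13-19% in the severe one, where withdrawal tracks the outcome itself. The direction reverses if outcome-tracking withdrawals fall in the glargine arm. These are illustrations, not predictions. The point is worth correcting because the loss is avoidable and the planned sensitivity analyses only partly cover it. It is not evidence that the trial's result is biased.

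**What to change.** Reconcile the disease-progression bullet in 7.2 with 7.1. State that a participant whose assigned insulin is stopped or changed remains in study follow-up, with the visits and CGM sensors already scheduled, and is analysed as randomized. Leave withdrawal of consent and the investigator's best-interest discretion in place, and leave every insulin decision with the treating clinician.

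On the CRF, record stopping of assigned insulin separately from stopping of follow-up. Much of this exists: 7.2 records the reason for study withdrawal, 6.4 asks about current insulin at each visit, and the deviation list in 10.1.10 has entries for stopping study medication and for cross-over. What is needed is an explicit pair of fields.

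The cost is a wording change, a small CRF change, and a few already-scheduled visits and sensors in participants who would otherwise have left. Some participants will be followed off their assigned insulin, which 7.1 already accepts. No procedure or patient is added.
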